#### 6.4.1.9 STUDY COMPLETION

This prospective interventional study is expected to be completed within 12 months. Participants who are recruited will only be involved up to 24 weeks of duration, but the prospective interventional study overall will be completed within 12 months when the final participant has had their final visit. Data analysis and submission of the primary manuscript will occur within 6 months of study closure. Participants involved in the study will receive ongoing care as per standard practice.

#### 6.4.2 STUDY SCHEDULE

A table of the visits schedule and study procedures is in Appendix 2.

Randomisation will occur prior to recruitment of participants.

The Investigator or his/her approved designee must explain the nature of the study protocol and associated risks to the potential study participant. The potential participant must be allowed to review the study information and to ask questions before being asked to sign the Informed Consent Form.

Signed informed consent must be provided by the potential study participant prior to initiation of any screening evaluations or other study-related procedures. The signature, date, and name of the individual at the site who obtained the informed consent will be recorded in the participant's source record. After written informed consent is obtained, a copy of the signed form will be provided to the patient to keep. The participant will then be assigned a participant number.

##### 6.4.2.1 SCREENING

All participants will be screened prior to enrolment in the study. The following procedures must be conducted at the screening visit.

- Written informed consent
- Review of eligibility (diagnosis, inclusion and exclusion criteria)
- Medical history (including previous psoriasis treatments)
- Physical Examination
- Vital Signs (Respiratory rate, heart rate, tympanic temperature, blood pressure)
- Weight
- Height
- HS severity score baseline measurements

##### 6.4.2.2 VISIT 1 (WEEK 0)

This visit occurs no later than 28 days from Screening visit. The visit may occur on the same day as the screening visit provided i) the participant was given sufficient time to read through the patient information and consent form and ii) seek advice from their primary physician, family and/or friend and iii) have had their questions answered by the investigator adequately.

- Review of inclusion and exclusion criteria

- Review of medical history
- Review of adverse events (if any)
- Concomitant medication collection
- Vital Signs (Respiratory rate, heart rate, tympanic temperature, blood pressure)
- Physical Examination
- Weight
- Review of HS progress
- Follicular unit extraction and sample analysis (if intervention group)
- HS severity score assessments

#### 6.4.2.3 VISIT 2 (WEEK 6)

- Review of withdrawal criteria
- Review of adverse events (if any)
- Review of HS progress
- Concomitant medication collection
- Vital Signs (Respiratory rate, heart rate, tympanic temperature, blood pressure)
- Physical Examination
- HS severity score assessments

#### 6.4.2.4 VISIT 3 (WEEK 12)

- Review of adverse events (if any)
- Review of HS progress
- Concomitant medication collection
- Vital Signs (Respiratory rate, heart rate, tympanic temperature, blood pressure)
- Physical Examination
- HS severity score assessments

#### 6.4.2.5 VISIT 4 (WEEK 24)

- Review of adverse events (if any)
- Review of HS progress
- Concomitant medication collection
- Vital Signs (Respiratory rate, heart rate, tympanic temperature, blood pressure)
- Physical Examination
- HS severity score assessments

### 6.5 STANDARD CARE AND ADDITIONAL TO STANDARD CARE PROCEDURES

Standard Care Procedures		
Procedure	Time/Visit	Dosage/Volume
Resorcinol 15%/topical clindamycin	Week 0	Applied to affected area as needed when there is flare.

Additional To Standard Care		
Procedure	Time/Visit	Dosage/Volume
FUE	Visit 1	NA

## 6.6 RANDOMISATION

A staff member of Sinclair Dermatology not involved in this study will randomise participants into the intervention and controlled group using the program from [www.randomizer.org](http://www.randomizer.org) in a 1:1 stratification ratio. The treatment group will be treated with follicular unit extraction. Due to the study design, investigators and participants are unable to be blinded as to which participants will be in the treatment or control group. As there will be 24 participants in this study, numbers 1-24 will be randomly allocated to either control or treatment group using [randomizer.org](http://randomizer.org) prior to recruitment of the study. Participants will then be allocated a number in the order in which they are recruited in the study and subsequently will be placed in the group that the number has been randomised into.

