#### 6.4.1.5 PHENOTYPE BASELINE

The HS of the participants will be documented in the screening visit to identify its phenotype as follicular vs inflammatory (See Appendix 1).

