#### 6.4.1.8 HIDRADENITIS SUPPURATIVA SEVERITY ASSESSMENT

As part of standard routine care, participants will have the Hurley Stage of their HS, nodule count and abscess count documented at baseline. This is part of standard routine care to assess whether treatment is effective, and it will also allow us to calculate the hidradenitis suppurativa clinical response (HiSCR). HiSCR is defined as a  $\geq 50\%$  reduction in inflammatory lesion count (abscesses and inflammatory nodules), and no increase in abscesses or draining fistulas when compared with baseline. Participants will also have their hidradenitis suppurativa-physician's global

assessment (HS-PGA) and International Hidradenitis Suppurative Severity Score System (IHS4) score documented in follow-up visits. Pain will be assessed using the numerical scale 30 (NRS30) pain score (See Appendix 1).

These assessments will be done at week 0, week 6, week 12 and week 24.

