## 7. STUDY POPULATION

This study will enroll male and female patients aged ≥18 years who are diagnosed with mild to moderate HS.

The study will consist of 24 recruited participants.

**Study Name:** Hidradenitis suppurativa treated with follicular unit excision: A 24-week prospective study

**Protocol Number:** FUEHS001

**Version & date:** version 1.3, dated 3rd February 2024

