## 9.2 POWER CALCULATIONS

This pilot study uses 12 participants in each group (intervention vs controlled) and results from this will allow us to calculate the sample size required for statistical power in future clinical studies.

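### The allocation is labelled stratified but is one plain list of 24 not stated to be 12 and 12, and the unadjusted test in 9.3 leaves a chance gap in Hurley stage or baseline score uncorrected

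*Protocol*

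**What the plan says.** **Allocation.** Section 6.6 has an uninvolved staff member randomise participants "in a 1:1 stratification ratio"; 6.4.1.6 uses the same wording. Neither names a stratification factor or a block size. The mechanism in 6.6 is that "numbers 1-24 will be randomly allocated to either control or treatment group" before recruitment starts. "Participants will then be allocated a number in the order in which they are recruited in the study", and the number determines the group.

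**Numbers.** Section 9.2 states: "This pilot study uses 12 participants in each group". Section 7 states: "The study will consist of 24 recruited participants". Section 6.4.1.1 gives a total of 20 instead, also at 1:1.

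**Data at entry.** Section 6.4.1.8 says that "participants will have the Hurley Stage of their HS, nodule count and abscess count documented at baseline". Under 6.4.1.5, each participant's disease "will be documented in the screening visit to identify its phenotype as follicular vs inflammatory". Severity scores are taken at screening and again at week 0 (6.4.2.1, 6.4.2.2, Appendix 2). Eligibility admits Hurley stage 1 up to 2A (7.2).

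**Analysis.** Section 9.3 and the synopsis name a paired t test for lesion counts and for changes in the scores. No covariate appears.

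**The concern.** Anyone reading 6.6 for the design features, such as an ethics committee or a later systematic reviewer, would record a stratified allocation. The mechanism in the next sentences cannot deliver one, because order of recruitment alone decides who gets which number.

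With 12 per arm, chance can put noticeably more Hurley II participants in one arm. By the protocol's own account this bears on the outcome. Appendix 1 defines Hurley II by tract formation, and the IHS4 there gives each draining tunnel 4 points. It also describes the inflammatory phenotype as the more severe one. The trial hypothesis (6.1) and secondary objective 2 (6.2) compare scores between the groups, so a gap in severity at entry feeds into the comparison of interest. The information needed to adjust for it is already collected, but the stated test cannot use it.

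The pilot is also meant to supply the inputs for later sample sizes (9.1, 9.2), so an avoidable disturbance of the group difference would carry forward.

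**Working it through.** **1. The plan's own figure.** 2 × 12 = 24, which agrees with 6.6, 7 and 9.1 but not with the 20 in 6.4.1.1 (10 per arm at 1:1). The protocol gives no effect size, SD, alpha or power, so nothing further can be reproduced.

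**2. Chance gap in Hurley stage under a fixed 12/12 list.** Let K of the 24 be Hurley II and let x of them fall in one arm. The arms then differ by |2x − K| participants. With C(24,12) = 2,704,156,

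P(gap ≥ 4) = Σ C(K,x) · C(24−K, 12−x) / C(24,12), summed over x with |2x − K| ≥ 4.

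K is not in the protocol; 6 to 12 is an assumed range. For K = 12: 2 × (245,025 + 48,400 + 4,356 + 144 + 1) = 595,852, and 595,852 / 2,704,156 = 22.0%.

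| Hurley II among 24 (assumed) | Gap of 4 or more (at least 33 percentage points) | Gap of 6 or more (at least 50 points) |
|---|---|---|
| 6 | 15.5% | 1.4% |
| 8 | 19.3% | 2.7% |
| 10 | 21.4% | 3.6% |
| 12 | 22.0% | 3.9% |

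**3. Chance gap in a continuous baseline score.** The difference between two arm means of 12 has SD √(2/12) = 0.41 in units of the score's SD. On a normal approximation, P(|difference| > 0.5 SD) = 22%.

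**4. What an analysis of changes does with such a gap.** Let ρ be the correlation between baseline and follow-up, with equal SDs (assumed). Given a baseline gap of 0.5 SD, the raw follow-up difference carries 0.5ρ. The difference in changes carries 0.5(ρ − 1). A model adjusted for baseline carries 0 in expectation. The variance ratio, adjusted model to change score, is (1 − ρ²) / [2(1 − ρ)].

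| ρ (assumed) | Raw scores | Changes | Adjusted | Variance, adjusted / change |
|---|---|---|---|---|
| 0.3 | +0.15 SD | −0.35 SD | 0 | 0.65 |
| 0.5 | +0.25 SD | −0.25 SD | 0 | 0.75 |
| 0.7 | +0.35 SD | −0.15 SD | 0 | 0.85 |

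Taking changes therefore does not neutralise a baseline gap. It subtracts the whole gap where only the fraction ρ would have carried through, and leaves a shift in the opposite direction. Adjustment removes that shift and, under these assumptions, reduces the variance by 15% to 35%.

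**The case against.** The strongest reply is that little here is a fault. Simple randomisation is unbiased, and a valid between-arm standard error already allows for chance imbalance. Many pilots of this size are not stratified. The word in 6.6 reads as a slip for allocation, since 6.4.1.1 describes the same division simply as 1:1. Eligibility stops at Hurley 2A and excludes extensive scarring, which narrows the range of severity. The probabilities above are two-sided, so a gap of 4 or more in FUE's favour has about half of them, 8% to 11%. Covariates, subgroups and sensitivity analyses are commonly left to a statistical analysis plan, which is not at hand.

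Most of this stands. The absence of strata is not a defect, and neither is the blank subgroup row in the synopsis. What remains is what the protocol itself states: a label that does not match the mechanism, a list whose 12/12 split is left implicit, and a named test with no place for a covariate. That last item is a method stated in the protocol, not a detail deferred elsewhere.

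A reader might go further and infer that the list is 24 independent draws, in which case exactly 12:12 would arise in only 16% of lists. The text does not support this: 6.6 says 1:1 and 9.2 says 12 in each group, so a fixed split is the natural reading and only needs to be stated.

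**Conclusion.** The point holds as a wording correction plus an inexpensive improvement to the stated analysis. The stratification wording is wrong in two places, and 6.6 should say that the list is exactly 12 and 12. With that fixed, the remaining risk concerns who is in each arm, not how many. A gap of 4 or more Hurley II participants has a probability of 15.5% to 22.0%, assuming 6 to 12 of 24 are Hurley II. That is a realistic chance but not the expected outcome, and the named test makes no adjustment for it. The residual shifts in the working also rest on an assumed ρ of 0.3 to 0.7.

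It would be tempting to conclude that such an imbalance would overwhelm the treatment effect. The protocol gives neither an effect size nor an SD, so there is nothing to measure it against, and that conclusion is not supported. Nor does the point show that the trial must be stratified.

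**What to change.** - **Sections 6.6 and 6.4.1.6:** call 1:1 an allocation ratio, delete the reference to stratification, and state that the list contains exactly 12 control and 12 treatment numbers. Reconcile the total of 20 in 6.4.1.1, because the length of the list depends on it.
- **Section 9.3, and the matching row of the synopsis:** make the between-arm comparison a two-group model, for example ANCOVA, adjusted for the baseline value of the score and for Hurley stage. Repeat it with phenotype in place of Hurley stage as a sensitivity analysis. This replaces the paired t test for the comparison of arms, which are separate groups of participants. HiSCR as defined in 6.4.1.8 is a yes/no response already set against baseline, so it needs a two-group comparison of proportions instead.

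Stratified permuted blocks of 2 and 4 are not recommended. In an unblinded single-site trial they would make upcoming allocations partly predictable, and incomplete blocks in two strata would no longer guarantee 12 and 12.

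The cost is a wording change and one or two degrees of freedom: with all 24 analysed, residual degrees of freedom fall from 24 − 2 = 22 to 24 − 4 = 20 with both covariates. No new data are needed.

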## 7.3 EXCLUSION CRITERIA

Participants fulfilling any of these criteria are not eligible for inclusion in this study:

1. Current treatment with antibiotics, retinoids, immunosuppressants or biologic agents at the discretion of the investigator/research team.
2. Extensive scarring.
3. Absence of terminal hairs in target areas.
4. Previous laser hair removal in target areas.
5. Pregnant or lactating women.

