### 8.3.4 DEFINITION OF SCREENING FAILURES

A “screening failure” is a participant from whom informed consent is obtained and documented in writing (that is, the subject or legally authorized representative as required by local law and regulations, and the participant’s carer has signed an informed consent form), but who has not commenced receiving the study medication.

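### The number that fixes the group appears to be issued at consent, before eligibility review and baseline scoring, with no release step described and a screening-failure definition that ignores allocation

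*Protocol*

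**What the plan says.** **Allocation list.** Protocol 6.6, repeated in 6.4.1.6, states that "numbers 1-24 will be randomly allocated to either control or treatment group using" an online randomiser, before recruitment starts. A staff member outside the study does this. Then "Participants will then be allocated a number in the order in which they are recruited in the study", and the number determines the group. Neither investigators nor participants are blinded.

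**Timing of the number.** Protocol 6.4.2 requires that "Signed informed consent must be provided by the potential study participant prior to initiation of any screening evaluations or other study-related procedures". After consent and the handing over of a copy of the form, it continues: "The participant will then be assigned a participant number". No second numbering system is described anywhere.

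**Timing of eligibility and baseline.** Protocol 6.4.2.1 places the eligibility review and baseline severity scores at the screening visit and says "All participants will be screened prior to enrolment in the study". Protocol 6.4.2.2 repeats the eligibility check and the scores at Visit 1, which falls within 28 days of screening and may be on the same day.

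**Judgement in eligibility.** Protocol 7.3 excludes extensive scarring, and excludes several current treatments "at the discretion of the investigator/research team".

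**Screening failure.** Protocol 8.3.4 defines this as someone who has given documented consent "but who has not commenced receiving the study medication". It does not distinguish before from after allocation.

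**Numbers.** Protocol 9.1 and 9.2 plan 24 participants, 12 per group. Section 8.4 rules out replacing those who withdraw.

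**The concern.** Randomisation protects a comparison only if the people who decide on entry and record baseline cannot know the next assignment while they do so. Generation of the list by someone uninvolved protects how the list is made. It does not by itself protect how each assignment is released.

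Here the order of steps lets the group be known before three judgements: whether scarring is extensive, whether current treatment disqualifies, and how many lesions are counted at baseline. The principal investigator is one of the two scorers (6.7). HiSCR is defined relative to the baseline lesion count (6.4.1.8), so a baseline count made with the group known feeds directly into an outcome.

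Two further consequences follow. A number given to someone later found ineligible may be lost from a list of only 24. A participant allocated to either group who does not start treatment fits the literal definition of a screening failure, and so may be removed under that label instead of being handled as a withdrawal.

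**Working it through.** **Step 1. Order of events on the natural reading.**

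1. The list for numbers 1-24 is made before recruitment (6.6).
2. Consent is signed (6.4.2).
3. The participant number is assigned (6.4.2); by 6.6 this fixes the group.
4. Eligibility is reviewed and baseline scores are taken at screening (6.4.2.1).
5. Eligibility is reviewed and scores are taken again at Visit 1 (6.4.2.2).

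The link between steps 1 and 3 assumes that the participant number in 6.4.2 is the allocation number in 6.6. That is likely, since no other number exists, but it is not stated.

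**Step 2. The competing reading.** If recruited in 6.6 means enrolled, then 6.4.2.1 puts screening first and section 7, which speaks of 24 recruited participants, would count only people who passed it. Numbering would then follow the screening visit. Even so, nothing places it after the Visit 1 eligibility check and Week 0 scores.

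**Step 3. The plan's own figure.** 12 + 12 = 24, so the stated total reproduces. No alpha, power, effect size or SD is given, so there is no sample-size formula to test.

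**Step 4. Size of the loss if numbers are used up at consent.** Let f be the share of numbered participants who are never treated. The protocol gives no value, so f is assumed at 5% to 30%. Assume also that numbers are not reissued, that losses are independent, and that f is the same in both groups.

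- Expected treated per group: 12 × (1 − f).
- After the 20% loss to follow-up mentioned in 9.1: 12 × (1 − f) × 0.8. With no numbers lost this would be 12 × 0.8 = 9.6.
- Chance of losing at least one number: 1 − (1 − f)^24.
- Chance that the groups differ by two or more: the sum of p(i)p(j) over |i − j| ≥ 2, with p the Binomial(12, f) probabilities.

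| f (assumed) | Treated in total | Treated per group | Per group after 20% loss | P(at least one lost) | P(groups differ by ≥2) |
|---|---|---|---|---|---|
| 5% | 22.8 | 11.4 | 9.1 | 0.71 | 0.14 |
| 10% | 21.6 | 10.8 | 8.6 | 0.92 | 0.29 |
| 20% | 19.2 | 9.6 | 7.7 | 0.995 | 0.44 |
| 30% | 16.8 | 8.4 | 6.7 | >0.99 | 0.50 |

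For example, at f = 5%, 1 − 0.95^24 = 0.708. Each participant lost from a group is 1/12, or about 8%, of it.

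**Step 5. Screening failure against withdrawal.** Section 8.3.4 turns only on consent given and treatment not started. Section 8.2.1 covers people who state an intention to withdraw and encourages final evaluations, so that their data are recorded like those of completers. Someone allocated to FUE who declines the procedure fits both, and the protocol does not say which applies.

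**The case against.** A reader might infer that allocation is simply not concealed. The documents do not say so. A staff member outside the study makes the list, and no passage says that investigators hold it, see it, or learn the group at consent. The statement that blinding is impossible concerns knowledge after assignment, not access to the next assignment. What stands is narrower: no release or concealment step is described, and the order of steps permits early knowledge.

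A reader might also infer that randomised participants drop out of the comparison. Section 8.3.4 is only a definition. It does not exclude anyone from follow-up or analysis, and section 8.2.1 offers a route with continued recording. The definition also speaks of medication, so how it applies to a surgical procedure is unclear. Analysis sets may be defined in a statistical analysis plan that is not shown, and their absence here is not a finding. The remaining fault is that the label can attach after allocation.

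It is tempting to add that losses will be heavier before surgery than before a topical treatment. That is plausible, but no figure in the protocol supports it, so the table assumes equal losses. Nor does section 8.4 settle what happens to the number of a screening failure: it concerns withdrawals, and reissue is not mentioned either way.

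Finally, this is an unpowered, open-label pilot whose later scores are also made with the group known. That limits how much an early release adds to existing bias at scoring. It does not excuse exposing eligibility decisions and the baseline, which can be protected even in an open-label trial.

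**Conclusion.** The point holds in a limited form. On the natural reading of 6.4.2 with 6.6, the group can be known before eligibility is judged and baseline is scored; 6.4.2.1 and section 7 allow another reading, and the passages must be reconciled. Twelve per group may not be reached, to the extent shown in the table, if numbers go to participants never treated and are not reissued. The size of any selection bias cannot be estimated from the protocol. Section 8.3.4 needs to separate failures before allocation from non-treatment after it.

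These are rules of trial conduct that the protocol itself sets, and a later analysis plan cannot undo an early release. Moderate confidence, because the identity of the two numbers and the time of disclosure are inferred. It should be fixed.

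**What to change.** - **6.4.2:** issue only a screening ID at consent, distinct from numbers 1-24.
- **6.6, and the matching text in 6.4.1.6:** state that the uninvolved staff member keeps the list and releases the next allocation, by sealed opaque envelope or phone call, only at Visit 1, after eligibility is confirmed and Week 0 scores are recorded. Reconcile the terms recruited and enrolled with 6.4.2.1 and section 7.
- **8.3.4:** define a screening failure as a participant who consents but is not allocated, so that those allocated but untreated stay in the trial and are followed up.

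All 24 numbers then go to participants confirmed as eligible. The number to screen is 24/(1 − f) rounded up: 26, 27, 30 or 35 for an assumed screen-failure share of 5%, 10%, 20% or 30%.

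The cost is wording and 24 envelopes or calls. The one drawback is that the FUE slot is confirmed slightly later when screening and Visit 1 fall on the same day.
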